6.6 Overdose

Any dose of study drug in excess of that specified in this protocol is considered to be an overdose. Signs and symptoms of an overdose that meet any Serious Adverse Event criterion must be reported as a Serious Adverse Event in the appropriate time frame and documented as clinical sequelae to an overdose. There is no specific antidote for ibrutinib. In the event of an overdose, subjects should be closely monitored and given appropriate supportive treatment.

7. CORRELATIVE STUDIES (COHORT A ONLY)

7.1 Molecular Monitoring for Minimal Residual Disease

Molecular monitoring using immunoseqMRD testing (refer to Study Schedule) will be done at pre-specified endpoints for CLL and MCL patients (cohort A) and will be considered as standard of care.

7.2 Molecular Monitoring in Presence of Relapse/Progression for CLL and MCL Patients (Cohort A)

Patients suspected of relapse or progression of disease typically undergo histological confirmation. If there is histological presence of disease, these samples from lymph node, BM or other areas will be sent for immunoseqMRD testing to try and identify any clonal shift at time of relapse. This may allow us to gain insight into mechanisms of ibrutinib and escape from GVT effect.

7.3 Molecular Studies for T-cell Repertoire Analyses Using IMMUNOSEQ

Molecular studies for T-cell repertoire analyses using IMMUNOSEQ will be considered a research test and will be done at pre-specified endpoints (refer to Study Schedule). This will be done in all patients in cohort A.

CyTOF Analyses

- For patients in CR (Cohort A): We will employ single-cell mass cytometry to gain a more complete understanding of the impact of ibrutinib on B cell subsets and signalling post SCT

- For patients in CR (Cohort A): We will employ single-cell mass cytometry to gain a more complete understanding of the impact of ibrutinib and GVHD on T cell subsets and signalling post SCT
- For patients with relapse/progression post HCT (cohort A): We will employ single-cell mass cytometry to gain a more complete understanding of the impact of ibrutinib on B cell subsets and identification of signalling pathways that escape BTK inhibition

CytoF studies will be coordinated by [name] Lab at Vanderbilt University

7.4 Correlative Sample Collection and Handling

The actual dates and time and appropriate laboratory parameters must be recorded in the electronic clinical trial database. **See the Laboratory Manual** for appropriate processing and shipping instructions.

8. CORRELATIVE STUDY DESCRIPTION

8.1 immunoseqMRD

immunoseqMRD analysis involves amplification of immunoglobulin heavy chain (IGH) loci using consensus V and J segment primers followed by high-throughput sequencing (HTS)³⁸, enabling quantification with a detection limit of one cell per million mononuclear cells. Both peripheral blood and marrow aspirate can be used for this assay. This next-generation sequencing method has been used with success for monitoring MRD in multiple lymphoid malignancies^{39,40}.

immunoseqMRD sequencing-based MRD assessment provides greater sensitivity compared to traditional MRD detection methods, such as flow cytometry and allele-specific oligonucleotide PCR approaches³⁸. Moreover, the prognostic value of MRD assessment by sequencing in patients with chronic lymphocytic leukemia⁴¹, multiple myeloma³⁹, acute lymphocytic leukemia⁴² and diffuse large B-cell lymphoma⁴³ has been demonstrated.

[name] and Stanford investigators pioneered immunoglobulin heavy chain high throughput sequencing (IGH-HTS) technologies to provide ultrasensitive CLL MRD detection^{44,45}. Minimal Residual Disease (MRD) was quantified by the commercially available CLONOSIGHT method (Sequentia) with a sensitivity of 1 CLL clone in a million blood WBC. Beginning at 9 months post-transplant, MRD detected at 10^{-6} or higher (at least one CLL clone per million PBMC genomes) indicates a significant risk of relapse⁴⁶. As shown in Figure 3, the one-year post allo-HCT detection of CLL by CLONOSIGHT is highly predictive of CLL relapse ($p=0.0002$).

[figure not shown]

Figure 3: Disease free survival is predicted by MRD (as detected by ClonoSIGHT) at 1 y post HCT

In patients with chronic GVHD, there is often production of alloreactive antibodies. This has been demonstrated by the [name] lab, using gender mismatch HCT as a model^{30;47;48}.

We propose to correlate the presence of HY antibodies with clonal diversity as measured by the Immunoseq assay.

8.2 Immunoseq

ImmunoSeq Assays illuminate the adaptive immune system with controlled Multiplex PCR amplification and high throughput sequencing of T-cell receptors combined with sophisticated bioinformatics.

8.3 CyTOF

Although B cell dysfunction has been implicated in the pathogenesis of chronic GVHD, the role of B-cell dysfunction in acute GVHD remains less well defined. Acute GVHD is typically thought of as a T cell mediated process, with complex interactions through antigen presenting cell (APC) populations, regulatory T cells (T regs), B cell immune response and cytokine secretion. Very recently, a new technology has been developed for the analysis of complex cell subsets, termed single-cell mass cytometry using the DVS CyTOF mass cytometer. Figure 4 shows a schematic of the CyTOF technology. This allows a systems level description of immune response through the simultaneous measurement of more than thirty cell surface marker proteins. The [name] lab has expertise in this technology and has used this assay in single cell interrogation in lymphoma and more specifically in BCR signalling⁴⁹⁻⁵¹.

[figure not shown]

Figure 4: Workflow of CyTOF technology. Cells in single cell suspension are labelled with antibody conjugates tagged to chelated elemental isotope. Each cell can be tagged with 34 probes and thus the output reflects 34+ dimensional single cell analyses. Both surface and intracellular targets can be interrogated.

Appendix 1: Figures 5 to 8 outline the utility of CyTOF in not only dissecting the BCR signaling network but also to generate 2 dimensional heat-maps of 34+ dimensional data. The [name] lab has proven expertise in B cell biology using CyTOF.

- We will employ single-cell mass cytometry to gain a more complete understanding of the impact of ibrutinib on B cell subsets and signalling post SCT

- We will employ single-cell mass cytometry to gain a more complete understanding of the impact of ibrutinib and GVHD on T cell subsets and signalling post SCT

It is anticipated that this may provide novel insights into the changes induced by ibrutinib on the immune system in the early post SCT period.

Samples will be analysed through a collaborative effort with Drs. [name] and [name] (both at Vanderbilt University). Single-cell mass cytometry will be used to analyse blood taken from patients prior to administration of ibrutinib, day 100 post SCT, and at month 6 post HCT. If patients develop new onset acute or chronic GVHD while on ibrutinib, an additional sample will be collected. We will objectively assess cellular heterogeneity from single-cell measurement data using an established computational approach, spanning-tree progression analysis of density-normalized events (SPADE) and ViSNE. In this work, we will ensure that all cell surface markers previously implicated in GVHD are included in the analysis. Single-cell mass cytometry will be carried out using the DVS CyTOF mass cytometer in the Flow Cytometry Core facility at Vanderbilt University. [name] laboratory has validated a B-cell panel to interrogate B cell dysfunction in the context of lymphoma (see Figures 6-8, Appendix 1). We expect that the same panel of B cell markers to give us adequate insight into the effect of ibrutinib on BCR signaling in the post-HCT period. In addition, we will interrogate cell subsets to include Th1, Th2, Treg, Th17, T effector cells, CD4+ T cell subsets (naïve, effector, memory, and central memory), antigen presenting cells, dendritic cells, and macrophages. Following core hematopoietic surface markers (12) have been validated by the (CD3, CD4, CD8, CD11b, CD19, CD20, CD38, CD45, CD45RA, CD90, CD123, HLADR). In addition, the following 15 markers are available (CD16, CD25, CD27, CD28, CD36, CD39, CD56, CD95, CD103, CTLA4, CD161, CD62L, CD14). Eight intracellular epitopes from mitogen pre-activated cells can be interrogated (IFN-gamma, TNF-alpha, IL-10, IL-17, FoxP3, IL-6, IL-4, and IL-13). This will allow us to get a complete picture of the interaction of ibrutinib on the T cell subsets in the post HCT setting.

9. ELIGIBILITY CRITERIA: INCLUSION

Pre-SCT

1. Adult (≥ 18 y) patients undergoing their first T cell replete allo-HCT for chronic lymphocytic leukemia (CLL), Hodgkin Lymphoma (HL), or the following subtypes of Non-Hodgkin lymphoma: Mantle cell lymphoma (MCL) and follicular center cell lymphoma (FL)
2. Meeting institutional criteria for allo-HCT. Ejection fraction by echocardiogram or MUGA $>40\%$, pulmonary function test with adjusted DLCO $\geq 60\%$
3. Matched (8/8) or mismatched (7/8) related, unrelated HCT
4. Stem cell source: bone marrow, peripheral blood stem cell
5. Disease criteria:

Cohort A:

CLL

- Disease burden: lymph node size <5cm and/or extra-nodal involvement <5 cm

AND

- 17 p deletion (detected by any assay) ($\geq 20\%$ of cells involved if assay is conventional cytogenetics or FISH) or NOTCH mutation at any time point during disease course. Patient should have received at least 1 line of therapy. Prior ibrutinib therapy is permitted.

OR

- Relapsed/refractory CLL ≥ 2 lines of therapy. Prior ibrutinib therapy is permitted

MCL

- Disease burden: lymph node size <5 cm and/or extra-nodal involvement < 5 cm
- Relapsed/refractory MCL ≥ 1 line of therapy. Prior ibrutinib therapy is permitted. Prior autologous HCT is permitted.
- MCL blastoid variant in CR1 or high risk MCL being considered for allo HCT in CR1

Cohort B:

FL

- Disease burden: lymph node size <5cm and/or extra-nodal involvement <5 cm

AND

- Relapsed/refractory FL ≥ 2 lines of therapy. Prior ibrutinib therapy is permitted.

HD

- Disease burden: lymph node size <5cm and/or extra-nodal involvement <5 cm

AND

- Relapsed/refractory HD ≥ 2 lines of therapy

6. Preparative regimen: both reduced intensity and ablative regimens are permitted. Each center will pre-specify the regimen they intend to use during the conduct of the study
7. Donor criteria: HLA $\geq 7/8$ related or unrelated donors.
8. Women of childbearing potential and men who are sexually active must be practicing a highly effective method of birth control during and after the study consistent with local regulations regarding the use of birth control methods for subjects participating in clinical trials. Men must

agree to not donate sperm during and after the study. For females, these restrictions apply for 1 month after the last dose of study drug. For males, these restrictions apply for 3 months after the last dose of study drug.

9. Women of childbearing potential must have a negative serum (beta-human chorionic gonadotropin [β -hCG]) or urine pregnancy test at Screening. Women who are pregnant or breastfeeding are ineligible for this study.
10. Sign (or their legally-acceptable representatives must sign) an informed consent document indicating that they understand the purpose of and procedures required for the study, including biomarkers, and are willing to participate in the study.
11. Prior to administration of ibrutinib (day 60 today 90 post HCT)
 - KPS \geq 60%
 - Engraftment of neutrophils (ANC \geq $1.0 \times 10^9/L$) for 3 days without g-CSF support
 - Platelets $\geq 100,000/mm^3$ or $\geq 50,000/mm^3$ if bone marrow involvement independent of transfusion support in either situation
 - GFR \geq 30 ml/min
 - LFTs (ALT and AST) $\leq 3 \times$ ULN; total bilirubin ≤ 1.5 mg/dL \times ULN unless bilirubin rise is due to Gilbert's syndrome or of non-hepatic origin
 - Predominant donor chimerisms of $\geq 51\%$ as measured by CD3 and CD33 (or other myeloid marker)

10. ELIGIBILITY CRITERIA: EXCLUSION

Pre-SCT

1. Progression of CLL or MCL or FL or HD at time of transplant
2. Use of Coumadin (warfarin) or other vitamin-K antagonists for anticoagulation. Non-coumadin anticoagulation is permitted.
3. Known CNS involvement
4. Active uncontrolled bacterial or invasive fungal infections
5. History of malignancy other than the underlying disease unless treated with a curative intent and/or no evidence of disease for at least 3 y OR expected to be cured with SCT
6. Planned use of post-HCT cyclophosphamide for GVHD prophylaxis
7. Anticipated planned donor lymphocyte infusion in the first 3 months post-SCT
8. T deplete HCT
9. Umbilical cord HCT
10. History of stroke or intracranial hemorrhage within 6 months of enrollment.

11. Clinically significant cardiovascular disease such as uncontrolled or symptomatic arrhythmias, congestive heart failure, or myocardial infarction within 6 months of Screening, or any Class 3 (moderate) or Class 4 (severe) cardiac disease as defined by the New York Heart Association Functional Classification.
12. Known HIV
13. Active Hepatitis B or C virus
14. Child-Pugh Class C

Prior to Administration of Ibrutinib (Day 60-Day 90 Post SCT)

1. In the critical care unit, or use of mechanical ventilation or use of renal replacement therapy at any time post HCT and prior to administration of ibrutinib
2. Active uncontrolled stage 3-4 acute GI GVHD prior to administration of ibrutinib
3. Active uncontrolled stage 4 acute liver GVHD prior to administration of ibrutinib
4. Evidence of progressive disease as compared to pre-HCT (persistence of disease is permitted)
5. Anticipated planned donor lymphocyte infusion in the first 3 months post-SCT
6. Active uncontrolled bacterial or invasive fungal infections
7. Prednisone equivalent of >2mg/kg for treatment of GVHD prior to administration of ibrutinib
8. Use of second line systemic therapy for treatment of acute GVHD prior to administration of ibrutinib
9. Any life-threatening illness, medical condition, or organ system dysfunction which, in the investigator's opinion, could compromise the subject's safety, interfere with the absorption or metabolism of ibrutinib capsules, or put the study outcomes at undue risk including the presence of chronic/active HBV and HBC infections and Child-Pugh Class C.
10. Major surgery or a wound that has not fully healed within 4 weeks of starting ibrutinib
11. Requires anticoagulation with warfarin or equivalent vitamin K antagonists (e.g., phenprocoumon).
12. Requires chronic treatment with strong CYP3A inhibitors
13. Vaccinated with live, attenuated vaccines within 4 weeks of starting ibrutinib

11. DOSE MODIFICATIONS

11.1 Dose Modifications for Adverse Reactions

Interrupt IMBRUVICA therapy for any Grade 3 or greater non-hematological, Grade 3 or greater neutropenia with infection or fever, or Grade 4 hematological toxicities. Once the symptoms of the toxicity have resolved to Grade 1 or baseline (recovery), IMBRUVICA therapy may be reinitiated at the starting dose. If the toxicity reoccurs, reduce dose by one capsule (140 mg per day). A second reduction of dose by 140 mg may be considered as needed. If these toxicities persist or recur following two dose reductions, discontinue IMBRUVICA.

The dose of ibrutinib will be modified according to the dose modification guidelines in the table below if any of the following toxicities occur:

Parameter for which dose is being modified	Dose modification duration	Dose restarting parameters	Dose to be restarted	Comments
Grade 3 ANC (<1,000/ μ L) with an associated temperature of $\geq 38.5^{\circ}\text{C}$	Hold ibrutinib	Restart after 7 days provided ANC $\geq 1,000/ \mu\text{L}$ and patient is afebrile for at least 72 hrs.	Level -1	If toxicity is felt to be due to ibrutinib
Grade 4 ANC (<500/ μL) for more than 7 days	Hold ibrutinib	Restart after 14 days provided ANC $\geq 500/ \mu\text{L}$ for at least 7 days	Level -2	If toxicity is felt to be due to ibrutinib
Grade 3 thrombocytopenia (<50,000/ μL) in the presence of Grade ≥ 2 bleeding events	Hold ibrutinib	Restart after 14 days provided platelet count $\geq 50,000/ \mu\text{L}$ and no bleeding for at least 7 days	Level -2	If patient is on concomitant anticoagulation therapy, stabilize the anticoagulation therapy (if it was restarted) before ibrutinib is restarted
Grade 4 thrombocytopenia (<25,000/ μL)	Hold ibrutinib	Restart after 14 days provided platelet count $\geq 50,000/ \mu\text{L}$ for at least 7 days	Level -2	
Grade 3 or 4 nausea, vomiting, or diarrhea if persistent, despite optimal anti-emetic and/ or anti-diarrheal therapy	Hold ibrutinib	Restart after 14 days provided toxicity is at grade 2 or lower for at least 7 days	Level-2	Acute or chronic GVHD may cause nausea, vomiting, diarrhea and needs to be ruled out. If toxicity is attributed to GVHD and resolves drug can be restarted at dose level -1. Similarly, diarrhea can be due to Clostridium difficile colitis-if yes, no dose

Parameter for which dose is being modified	Dose modification duration	Dose restarting parameters	Dose to be restarted	Comments
				reduction may be necessary
Any other Grade 4 or unmanageable Grade 3 toxicity attributed to ibrutinib	Hold ibrutinib	Discontinue drug (level -3)	Not applicable	None

Dose Levels:

- Dose level 0 = 420 mg po qd
- Dose level -1 = 280 mg po qd
- Dose level -2 = 140 mg po qd
- Dose level -3 = discontinue drug

For patients starting with 140 mg qd (due to concomitant moderate CYP3A inhibitor or azole use as outlined in section 11.2)

- Dose level 0 = 140 mg po qd
- Dose level -1 = 70mg po qd
- Dose level -2 = 70 mg po qod
- Dose level -3 = discontinue

If a patient was on 140 mg po qd (due to concomitant azole use) and then stopped azole, the dose will be increased to 420 mg po qd. This will not be considered a dose escalation.

For patients starting with 70 mg qd (due to concomitant Posaconazole use as out lined in section 11.2)

- Dose level 0 = 70 mg po qd
- Dose level -1 = 70 mg po qod
- Dose level -2 = discontinue

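### Section 11.1's paragraph and table give different first-event restart doses and recovery thresholds, the table's precedence is implied but not stated, and the paragraph's 140 mg reductions do not fit patients who start at 140 mg or 70 mg.

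*Combined protocol and SAP*

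**What the plan says.** The section 11.1 paragraph starts with the trigger "Interrupt IMBRUVICA therapy for any Grade 3 or greater non-hematological", and adds neutropenia of at least Grade 3 with fever or infection, and Grade 4 hematological toxicity. Recovery is set by "Once the symptoms of the toxicity have resolved to Grade 1 or baseline (recovery". After that, "IMBRUVICA therapy may be reinitiated at the starting dose. If the toxicity reoccurs, reduce dose by one capsule (140 mg per day". For a further step, "A second reduction of dose by 140 mg may be considered as needed".

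The next sentence introduces a table: "The dose of ibrutinib will be modified according to the dose modification guidelines in the table below if any of the following toxicities occur". The table has six rows and acts at the first event. One row (febrile Grade 3 ANC) restarts at level −1. Four rows restart at level −2: Grade 4 ANC lasting over 7 days, Grade 3 thrombocytopenia with bleeding, Grade 4 thrombocytopenia, and persistent Grade 3–4 nausea, vomiting or diarrhea. The last row discontinues the drug for other Grade 4, or unmanageable Grade 3, toxicity attributed to ibrutinib.

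Some rows carry qualifiers. Both ANC rows note "If toxicity is felt to be due to ibrutinib". The gastrointestinal row's recovery condition is "Restart after 14 days provided toxicity is at grade 2 or lower for at least 7 days", and its comments add "If toxicity is attributed to GVHD and resolves drug can be restarted at dose level -1" and relax the reduction for C. difficile. The Grade 4 thrombocytopenia row has no comment.

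Separate dose-level lists follow for patients starting at 420, 140 and 70 mg. Section 11.2 expects most patients to be on azoles until day 100, hence at 140 mg, with a rise to 420 mg when the azole stops.

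**The concern.** Sites must act on one rule when a transplant recipient has a severe toxicity, and section 11.1 offers two that disagree on both the restart dose and how much recovery is needed. For the group that section 11.2 expects to be the largest at the outset, the paragraph's reduction step cannot be carried out at all.

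The statistical stake is modest but real. Safety and tolerability are a secondary objective in both cohorts, and section 25.1 tabulates reasons for discontinuation. The table's last row stops the drug where the paragraph would allow a restart, so the discontinuations reported would depend partly on which rule a site followed.

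**Working it through.** **Inputs.** Paragraph steps of 140 mg, used up to twice, from section 11.1. Dose levels 0, −1, −2 from the lists under the table: 420/280/140 mg daily; 140 mg daily, 70 mg daily, 70 mg every other day; 70 mg daily, 70 mg every other day, discontinue. Taking 70 mg every other day as an average of 70/2 = 35 mg/day.

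**Paragraph reductions against the ladders** (first step = start − 140; second = start − 280):

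| Start | Paragraph steps | Levels −1, −2 | Agree? |
|---|---|---|---|
| 420 mg | 280, 140 mg | 280, 140 mg | Yes |
| 140 mg | 0, −140 mg | 70, 35 mg/day | No |
| 70 mg | −70, −210 mg | 35 mg/day, discontinue | No |

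The paragraph reproduces the 420 mg ladder exactly and cannot be applied to the other two.

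**Restart dose after a first Grade 4 thrombocytopenia** (a row with no attribution qualifier, and plainly a Grade 4 hematological toxicity under the paragraph; table level −2):

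| Start | Paragraph (permitted) | Table | Ratio |
|---|---|---|---|
| 420 mg | 420 mg | 140 mg | 420/140 = 3 |
| 140 mg | 140 mg | 35 mg/day | 140/35 = 4 |
| 70 mg | 70 mg | discontinue | – |

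**Which rows overlap the paragraph.** Febrile Grade 3 ANC, Grade 4 ANC over 7 days, Grade 4 thrombocytopenia and persistent Grade 3–4 gastrointestinal toxicity all meet a paragraph trigger. The last row does so for any Grade 4 event and for non-hematological Grade 3 events. Grade 3 thrombocytopenia with bleeding does so only if the bleed is itself Grade 3 or higher.

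**Recovery thresholds.** The paragraph waits for Grade 1 or baseline. The gastrointestinal row accepts Grade 2. The Grade 4 ANC row accepts 500/µL or more; the table itself labels ANC below 1,000/µL as Grade 3, so 500 to 999/µL is still Grade 3 there, and section 9 required 1.0 × 10⁹/L (1,000/µL) to start ibrutinib.

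**70 mg starters under the table.** Four rows tell the site to restart at level −2, which for these patients is defined as discontinuation.

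**Hepatic impairment.** Section 11.3 says to avoid ibrutinib in Child-Pugh classes B and C. The pre-ibrutinib exclusion in section 10 and in the synopsis names only class C.

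**The case against.** The strongest reply is that precedence is all but given. The paragraph is permissive (*may*) and the table's lead-in is mandatory (*will*). A site that restarts at the table dose breaches nothing, while one that restarts a listed event at full dose departs from the lead-in. This stands: the table is the natural governing rule, and a reader should not infer that the two rules have equal force. What remains is that the override is left to inference, and that giving the table priority does not settle what the paragraph still covers or mend its 140 mg steps.

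The table's thresholds also come with offsets that the paragraph lacks. The Grade 4 ANC and gastrointestinal rows require a 14-day hold, 7 days of sustained recovery and a restart at level −2. This too stands.

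Three stronger readings are tempting and are not supported:

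- *The last row inverts severity*, by stopping the drug for a short Grade 4 ANC while a longer one restarts. The natural sense of that row is toxicities other than those already listed. A Grade 4 ANC of 7 days or less then falls to the paragraph, or to row 1 if febrile, since a count below 500 is also below 1,000.
- *A patient raised to 420 mg stays on the 140 mg ladder.* That ladder is tied to concurrent inhibitor use and has 140 mg as level 0. A patient on 420 mg without an azole fits the default ladder.
- *Child-Pugh B is unguarded.* Section 11.3 itself says to avoid it, and exclusion 9 covers organ dysfunction that could compromise safety or ibrutinib metabolism. The bilirubin and ALT/AST limits screen further. The mismatch is real but minor.

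**Conclusion.** The point holds as a drafting fault in a patient-safety rule. For the same first event the two parts of section 11.1 differ 3-fold for a 420 mg starter and 4-fold for a 140 mg starter, and differ between 70 mg daily and stopping for a 70 mg starter. These are the gaps that arise if a site follows the paragraph for a listed event; they assume Grade 4 thrombocytopenia and an average of 35 mg/day for alternate-day 70 mg. The failure of the 140 mg steps at the two lower starting doses needs no assumption.

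The 500/µL restart level is a fair query for the clinical team. A reader might infer that it is an error, but the documents give no restart data that would settle a threshold, and the longer hold and lower dose are part of the same rule.

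A reader might also try to count affected patients from section 6.3.3. Those figures do not allow it: the cytopenia rates pool Grades 3 and 4 in hematologic malignancies, whereas most table rows need Grade 4, fever, bleeding, duration or persistence. The chronic GVHD data do not list either cytopenia among Grade 3–4 events above 5%, and their overall discontinuation rate says nothing about this conflict.

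The consequence is confined to dosing safety and descriptive tolerability results. Section 25.1 plans no formal safety testing, and no power or sample-size figure changes.

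**What to change.** Amend section 11.1, with one matching eligibility change:

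1. State that the table governs the toxicities it lists, keeping the GVHD and C. difficile comments. Limit the paragraph to unlisted events; listed parameters below the table's threshold, such as Grade 4 ANC of 7 days or less (row 1 applying if febrile); and events not attributed to ibrutinib where the row requires attribution.
2. Replace both 140 mg reductions with *reduce by one dose level*, on the ladder for the patient's current CYP3A-inhibitor status, so that a patient raised to 420 mg uses the 420 mg ladder.
3. State that, for 70 mg starters, the level −2 rows mean permanent discontinuation.
4. Add Child-Pugh class B to the pre-ibrutinib exclusion in section 10 and the synopsis, to match section 11.3.

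Ask the clinical team to confirm or revise the 500/µL restart level; this is a query and not a required change.

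The cost is amendment wording, one eligibility-checklist line and a notice to sites. No extra patients, visits or tests are needed.

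### Section 11.1 fixes one restart level per toxicity whatever the current dose, so a patient at Level -2 with febrile Grade 3 neutropenia would, read literally, restart at twice the dose

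*Combined protocol and SAP*

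**What the plan says.** Section 11.1 has three parts.

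**Opening paragraph.** Ibrutinib is interrupted for non-hematological toxicity of Grade 3 or worse, for Grade 3 or worse neutropenia with infection or fever, and for Grade 4 hematological toxicity. After recovery, "IMBRUVICA therapy may be reinitiated at the starting dose". A recurrence brings a reduction of one 140 mg capsule, and a second such reduction is optional. The paragraph ends: "If these toxicities persist or recur following two dose reductions, discontinue IMBRUVICA".

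**Table.** It is introduced by "The dose of ibrutinib will be modified according to the dose modification guidelines in the table below if any of the following toxicities occur". Five rows carry a restart level:

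- Febrile Grade 3 neutropenia restarts at Level -1 after 7 days, provided that the ANC is back to at least 1,000/µL and the "patient is afebrile for at least 72 hrs". The comment reads "If toxicity is felt to be due to ibrutinib".
- Grade 4 neutropenia beyond 7 days, Grade 3 thrombocytopenia with bleeding, Grade 4 thrombocytopenia and persistent Grade 3-4 gastrointestinal toxicity all restart at Level -2 after 14 days.
- The gastrointestinal row adds a comment: "If toxicity is attributed to GVHD and resolves drug can be restarted at dose level -1".

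**Dose levels.** There are three ladders, set by the starting dose. Levels 0, -1 and -2 are 420, 280 and 140 mg daily; or 140 mg daily, 70 mg daily and 70 mg every other day; or 70 mg daily, 70 mg every other day and discontinue. A patient on 140 mg because of an azole goes to 420 mg when the azole stops, and the text says that this does not count as escalation.

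**The concern.** A toxicity table should never return a patient to more drug than they were taking when the toxicity occurred. This one fixes the restart level by type of event alone. It has no column for a second event, and no sentence in 11.1 caps the restart dose at the dose held before the event. For a patient already reduced to Level -2, a row that says Level -1 points upward.

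The sequence can arise from the protocol's own rules. Prolonged Grade 4 neutropenia moves a patient from Level 0 to Level -2 in one step, and allows restart once the ANC has been at least 500/µL for 7 days. The table defines Grade 3 as below 1,000/µL. The patient can therefore resume drug with a count that is still Grade 3, and a temperature of 38.5°C then meets the febrile Grade 3 row.

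At stake is the dose given after a second serious toxicity, and whether two sites that both follow the section would dose the same patient alike.

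**Working it through.** There is no plan figure to reproduce. The check sets every restart row against every dosing level on each ladder.

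**Inputs** (Section 11.1, table and dose-level lists), in mean mg/day, with every-other-day dosing counted as half:

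| Ladder | Level 0 | Level -1 | Level -2 |
|---|---|---|---|
| 420 mg | 420 | 280 | 140 |
| 140 mg | 140 | 70 | 35 |
| 70 mg | 70 | 35 | discontinue |

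**Formula:** ratio = dose at the row's restart level / dose held before the event. A ratio above 1 is an increase.

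**Febrile Grade 3 neutropenia (restart at Level -1):**

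- 420 mg ladder: from Level 0, 280/420 = 0.67; from Level -1, 280/280 = 1.0; from Level -2, 280/140 = **2.0**.
- 140 mg ladder: from Level 0, 70/140 = 0.5; from Level -1, 70/70 = 1.0; from Level -2, 70/35 = **2.0**.
- 70 mg ladder: from Level 0, 35/70 = 0.5; from Level -1, 35/35 = 1.0. Nobody is on drug at Level -2, so no increase is possible.

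**GVHD comment in the gastrointestinal row (Level -1 permitted):** the same ratios, including 2.0 from Level -2 on the 420 mg and 140 mg ladders. It says the drug can be restarted there, not that it must be.

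**The four Level -2 rows:** every ratio is 1.0 or less.

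**Does other text stop the increase?**

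- *Discontinuation sentence.* It needs toxicities that persist or recur after two reductions. Four of the five restart rows take a Level 0 patient on the 420 mg or 140 mg ladder to Level -2 in one move. The text does not say whether that counts as one reduction or two, or whether a different second toxicity counts as a recurrence.
- *The rest of the paragraph.* For a first occurrence it permits the starting dose, which is higher still.
- *Last table row.* It covers other toxicities, so it does not apply to those already listed.
- *Section 21.1.* Withdrawal requires more than 28 continuous days off drug. These rows allow restart after 7 or 14 days, so the limit need not be reached.
- *Section 26.4.* Deviations are allowed only to remove an immediate hazard, so a site cannot freely choose a different dose from the one in the table cell.

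**Paragraph against table at a first event.** For an event that meets both texts, the dose the paragraph permits divided by the table's dose is:

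- 420 mg ladder: 420/280 = 1.5 or 420/140 = 3.0.
- 140 mg ladder: 140/70 = 2.0 or 140/35 = 4.0.
- 70 mg ladder: 70/35 = 2.0, or discontinue.

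These compare a permitted ceiling with a required level; they are not two equal instructions. Recovery criteria differ as well: the paragraph asks for Grade 1 or baseline, while the gastrointestinal row says "Restart after 14 days provided toxicity is at grade 2 or lower for at least 7 days".

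**One-capsule step.** 140 - 140 = 0 mg, and 70 - 140 is negative. The paragraph's step therefore works only on the 420 mg ladder.

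**The case against.** The strongest reply is that the section, read as a whole, already prevents the increase. The discontinuation sentence speaks of these toxicities in the plural, which most naturally means the whole class named at the start of the paragraph, febrile neutropenia included. On the 420 mg ladder, 140 mg is exactly two 140 mg reductions, so stopping is the natural next step. Elsewhere the protocol raises the dose only when an interacting drug stops, and says so explicitly. An investigator would probably take a negative level to mean a reduction. Toxicity reviews, two safety calls a month and withdrawal by investigator decision offer further protection.

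Much of this is fair. It shows that the safer reading is available and likely. It does not make that reading the stated rule: the one-step route to Level -2 and a different second toxicity remain open, and no sentence sets a cap.

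Three stronger readings are tempting, and the documents do not support them.

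- *That nothing indicates which text governs at a first event.* The table is introduced with will and the paragraph's restart with may, so a site that uses the table's level breaches neither. The overlap is also limited by the rows' own conditions: duration beyond 7 days for Grade 4 neutropenia, persistence despite optimal therapy for gastrointestinal events, and attribution to ibrutinib for both neutropenia rows. What is missing is an explicit statement of precedence.
- *That the one-capsule step leaves patients on the lower ladders without a rule.* The separate ladders for 140 mg and 70 mg starters largely settle this.
- *That patients on the 70 mg ladder would wrongly resume drug.* Four rows say restart at a level defined as discontinue, but the default is to stop, which is conservative.

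**Conclusion.** The point holds as a gap in a safety rule. Read literally, one table row doubles the dose (2.0 times) for a patient at Level -2 on the 420 mg or 140 mg ladder who has febrile Grade 3 neutropenia attributed to ibrutinib. The GVHD comment permits the same increase. The discontinuation rule can be read to block it but does not clearly do so. The unstated precedence between paragraph and table is a lesser matter, because the wording already favours the table.

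This rests on taking the restart levels as the absolute doses in the lists, on a mean of 35 mg/day for 70 mg every other day, and on the site attributing the neutropenia to ibrutinib.

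A reader might infer that patients will often be re-escalated, or that the efficacy result is compromised. Neither follows. The documents give no frequency for these sequences, and no effect on the primary PFS analysis is shown. It should be fixed because the correction is small and the rule concerns dosing after serious toxicity.

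**What to change.** Add two statements to Section 11.1:

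(a) On the same ladder, the restart dose is never above the dose held before the event, including under the GVHD comment. The change of ladder when an azole stops stays as written.

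(b) The table governs wherever it differs from the opening paragraph, and the 140 mg step applies only to the 420 mg ladder.

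Under (a), a Level -2 patient with febrile Grade 3 neutropenia could resume at no more than 140 mg daily (420 mg ladder) or 70 mg every other day (140 mg ladder). The ratio is then at most 1.0, and both doublings are removed. Statement (b) would also make the table's recovery criteria prevail, so the sponsor should confirm that this is intended.

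Two matters are for the sponsor's clinical team: whether a patient already at a row's level should step down further or discontinue, and how to reword the restart instruction on the 70 mg ladder, where the conservative default is to stop.

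The cost is one edit in a protocol amendment and a memo to sites, with no extra patients or procedures.
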